WHO	World Health Organization

PROTOCOL SUMMARY

Title:	Family Intervention With Caregivers Of Children With Dental Needs
Précis:	The study is a multi-site, double blind, parallel arm, community-based randomized controlled trial (phase III RCT) to evaluate the effectiveness of new referral approaches to increase receipt of dental care among inner-city urban and rural elementary school children who were screened at school and have restorative treatment needs. The study has 5 arms: The experimental intervention is the use of a theoretically driven CSM referral letter alone, the CSM letter plus a Dental Information Guide, a reduced CSM referral letter alone, or a reduced CSM referral letter plus a reduced Dental Information Guide. The control strategy is the use of a modified standard referral letter. All RCT participating K-4 grade children will receive a screening at the beginning of the school year and at the study end point 7 months later to determine if the child received dental care.
Objective	
Primary: To evaluate the effectiveness of experimental (new) versus standard referral approaches given to parents/caregivers in increasing receipt of dental care among their children in grades K-4.
 
Secondary: To assess changes in parent/caregiver illness representation/perception and behavioral intention between enrollment (beginning of school year), 2-week and 7-month follow-up (end of school year) to understand the underlying mechanisms of the new vs. standard referral approach that result in receipt of dental care.

Population:	Population information: sample size=660 caregivers to be randomized; children will be both male and female, grades K-4; inner city African Americans (Bedford and E Cleveland, OH) and rural Whites and Hispanics (Cowlitz and Lewis counties, Washington State).
Phase:	III
Number of Sites:	
(1) East Cleveland City School District (ECCSD, Cleveland, OH), and Bedford City School District (BCSD, Bedford, OH).
 
(2) Cowlitz County (CCSD, WA), and Lewis County (LCSD, WA).

Description of Intervention:	The experimental intervention is the use of a theoretically driven CSM referral letter alone or the letter plus a dental information guide. The control strategy is the use of a modified standard referral letter.
Study Duration:	10 months
Subject Participation Duration:	1 year

Estimated Time to Complete Enrollment: 3 months

SCHEMATIC OF STUDY DESIGN

2. INTRODUCTION: BACKGROUND INFORMATION AND SCIENTIFIC RATIONALE

2.1 Background Information

The impetus for the proposed behavioral intervention trial comes from a community-based caries prevention trial among low-income minority kindergarten children followed until 2nd grade. During baseline exams, referrals were given for needed restorative and urgent care to the children's caregivers, but on a subsequent dental exam only 19% of the children had received care (Nelson et al. 2012). Standard letters and follow-up phone calls were not effective in improving dental attendance. Recent studies in the U.K. have also concluded that school screening is ineffective in stimulating subsequent dental visits (Milsom et al. 2006a, b). Thus, indications are that caregiver-level engagement or action is necessary to take care of their child's further dental needs without which the benefits of child-level screening or interventions at schools are not realized.

The experimental intervention will be based upon the Common Sense Model of Self-Regulation (CSM: Leventhal et al. 2003) to address parent/caregiver illness perception and navigation of resources to increase receipt of dental care during a 7-month follow-up period for children with restorative dental needs. In this five arm study the new CSM theory-driven referral letter alone or the new CSM referral letter and dental information guide (facts about dental caries, hints for getting dental care, making appointments and Medicaid access, transportation and dentists availability resources) will each be compared to a modified standard referral letter (based on November 2007 guidelines for Oral Health Screening in Ohio Schools) to increase receipt of dental care among inner-city urban African American, and rural Hispanic and White elementary school children.

The literature is clear that most low-income caregivers do not initiate and maintain the self-management strategies necessary for their children's oral health when the children are screened and referred from school. Most see dental diseases as acute, to be responded to only when there is pain or visible decay (Hooley et al. 2012). One approach used in self-management of chronic medical conditions is the Common Sense Model of Self-Regulation (CSM: Leventhal et al. 1997; Leventhal et al. 2003). This approach has never been used in dentistry. The CSM has been used to develop interventions for diabetes (Keogh et al. 2007; McAndrew et al. 2008), asthma (McAndrew et al. 2008), attendance for cardiac rehab (Mosleh et al. 2009), and primary care (Phillips, Leventhal & Leventhal 2012). The CSM proposes that in response to a health threat, people form a cognitive and emotional representation (perception) of their illness that guides coping and action planning, followed by an appraisal of the coping strategy. Five key constructs guiding the illness representation or perception are: Identity, the patient/caregiver labeling of disease and its symptoms; Cause, the individual's perception of the underlying cause of their illness; Consequence, the belief about the impact of the illness physically and socially; Timeline, the personal beliefs about the illness being acute, chronic, or cyclical in nature; and Cure or controllability, the belief whether the illness can be cured or kept under control by the individual or others. The importance of these concepts is that they are readily alterable, as opposed to many other factors in the system. The Illness Perception Questionnaire (IPQ: Weinman et al. 1996; Moss-Morris et al. 2002) has been used to identify these five dimensions of illness representation, together with coherence and emotional representation. A

CSM theory-based letter and information leaflet have been successfully shown to improve cardiac rehab attendance (Mosleh et al. 2009; Sniehotta et al. 2010). Other approaches such as motivational interviewing (MI) have been successful in reducing caries and influence positive behavior change among caregivers (Weinstein et al. 2006) but include multiple counseling sessions that are difficult and expensive when working with low-income populations and are likely not sustainable.

Dental caries is the leading chronic childhood disease (US DHHS 2000). Its prevalence is steadily increasing, with poor and minority children bearing the brunt. Among 2-11 year-olds, 64% of African American children, 60% of Mexican American children, and 50% of White children had untreated tooth decay (Dye et al. 2007). Nevertheless, despite availability of Medicaid, median dental utilization of low-income children is only 33-37% among the states (Hakim et al. 2012; GAO-08-1121, 2008). This trend highlights why so many children require extensive treatment under general anesthesia (Savage et al. 2004). Untreated primary teeth are a strong predictor of future caries indicating the chronicity of the disease (Birkeland et al. 1976; Bader et al. 1986; Van Palenstein et al. 2001; Motohashi et al. 2006). Untreated decay can lead to serious infections and pain, interference with eating/speaking, overuse of EDs, and lost school time (Edmunds et al. 1998). Early preventive care has been shown to reduce later downstream costs (Savage et al. 2004). Poorer oral health-related quality of life was found among preschoolers with ECC (Leal et al. 2012; Martins-Junior et al. 2012; Kramer et al. 2013) and among school children from low-income households (Locker 2007).

Twelve states mandate dental screening of school children. But, the laws do not require tracking and evaluation of children who receive referrals (ASTDD 2008). School screening has also been endorsed by W.H.O. (2003). This is seen as an antidote to prevalent parental views about lack of need for preventive care or treatment of children's decayed but asymptomatic teeth (Milgrom et al. 1998; Riedy et al. 2001; Tickle et al. 2003; Hilton et al. 2007). Recently, Nelson et al. (2012) found 19% dental utilization after school screening, referral, and parental reminders. Studies in the U.K. have also failed to demonstrate the effectiveness of screening (Milsom et al. 2006a,b). A related qualitative study by the same group found the school examination process was acceptable to parents and staff, but the procedure for follow-up was judged inadequate (Tickle et al. 2006). In contrast, other studies with follow-up (Zarod & Lennon 1992; Donaldson & Kinirons 2001; Hebbal & Nagarajappa 2005) reported increases in dental attendance. However, the rate was low even when the care was free; complex factors were involved in the receipt of follow-up care (Hebbal & Nagarajappa 2005). AAPD (2012) policy on school entrance oral examination states such exams are insufficient without follow-up.

2.2 Rationale

First, the new intervention letter addresses two core issues: (a) importance of caries-free primary teeth for protection of permanent teeth and, (b) viewing dental caries as a chronic disease rather than acute or episodic. The current scientific evidence is clear that low-income caregivers do not know the importance of taking care of primary teeth and have the belief that dental caries is present only when the child has pain or symptoms. National surveys also indicate that untreated cavities are disproportionately higher and dental access is lower among Medicaid-eligible children. Therefore, caregivers require an accurate perception of dental caries for them to self-manage their child's cavities and to adopt and maintain healthy behaviors. Hence our rationale for the use of the Common Sense Model of Self-Regulation (CSM) in attempting to change cognitive representation of the 2 core caregiver issues. The text of the intervention letter from the identity construct to timeline

construct is a chain of reasoning aimed at giving information and helping caregivers understand children's dental disease. Second, the new intervention letter also addresses a third core issue, resources to self-manage their child's cavities. For the resources component, the Dental Information Guide (DIG) will address the need for adequate knowledge of resources.

The difficulty that all dental screening programs face, and the one we propose to address, is that few low-income caregivers take their children who have been screened to the dentist for follow-up restorative care.

2.3 Potential Risks and Benefits

2.3.1 Potential Risks

There is no known risk with being in this study. However, some people may feel uncomfortable answering personal questions for research. We will try to make them feel as comfortable as possible and allow them to skip any questions that they choose not to answer. Confidentiality risks may exist if information is misplaced. We will take every precaution to protect participant information and keep it confidential. The child may still receive medical and dental care if the caregiver or the child decides not to be in this study. The dental exam is commonly done in a dental office.

2.3.2 Potential Benefits

The child may benefit if the caregiver learns about his/her tooth problems. If the child has tooth decay, we will give the caregiver a referral to a dentist or dental clinic for dental care. The child may also benefit by learning how to take care of his/her teeth.

3 OBJECTIVES

3.1 Study Objectives

The aim of this study is to evaluate the effectiveness of new referral approaches to increase receipt of dental care among inner-city urban and rural elementary school children who were screened at school and have restorative treatment needs. The primary outcome is the assessment of dental care receipt through dental exams. The secondary outcomes are change in caregiver illness perception, measured through the IPQ-RD, and behavioral intention measured through items in the caregiver questionnaire.

3.2 Study Outcome Measures

Table 3.2.1 shows a summary of the study outcome measures, their sources, and timeline.

3.2.1 Primary Outcome Measures

The primary outcome will be receipt of dental care based on a change determined by clinical examination between baseline and follow-up at study exit (7 months after baseline). Please see MOP Section 5.2 for details of dental exam and criteria.

In addition, other proximal surrogate outcomes from the caregiver questionnaire will also be assessed. These questions include: whether the child visited the dentist after the dental screening, the name of the dentist/dental clinic, whether an appointment was made or not, whether the child completed the needed dental treatment, the number of visits that were made to complete dental treatment, and if they did not complete the treatment the reasons why they did not complete the treatment.

Examiner Training and Calibration: Exams will be conducted in a portable dental chair in the schools by a trained/calibrated examiner. [name] will train/calibrate the examiners in the ICDAS protocol in a 4-day central training session. Detailed caries assessment and examiner training, calibration and reproducibility protocols are in the MOP (Section 5.2). Examiners will not utilize dental radiographs. At follow-up, the examiner will not have access to the results of the first examination to avoid detection bias.

3.2.2 Secondary Outcome Measures

The first secondary outcome (mediator) will be change in the overall Illness Perception Questionnaire-Revised for Dental (IPQ-RD), cognitive (identity, consequences, timeline, cause, cure/controllability) representation subscale scores (Weinman et al. 1996; Barrowclough & Lobban 2001; Moss-Morris et al. 2002; Bonetti et al. 2010).

The other secondary outcome (mediator) will be a change in behavioral intention (Luzzi & Spencer, 2008; Ajzen, 1991, 2002). Behavioral intention will be assessed using a caregiver questionnaire and is measured by the summative score of 2 items (e.g., “I want to take my child to the dentist”, and “I plan to take my child to the dentist” on a 5 point scale (Luzzi & Spencer, 2008). The use of these measures will allow us to better understand the mechanisms of action of the intervention based on

our conceptual model. The change in IPQ-RD and behavioral intention scores will be calculated between baseline, two week, and final follow-up. A decrease in IPQ-RD scores (i.e. lower score) indicates better illness representation/perception, while increase in behavioral intention scores indicate a higher intention to take the child to dentist for follow-up care.

Table 3.2.1 Summary of measures, timeline, and source

Variable Type	Measure	Timeline ¹	Source
Exposure (Intervention Study Arms)	
 • CSM referral letter alone • CSM referral letter + DIG • Reduced CSM referral letter alone • Reduced CSM referral letter + DIG • Modified Standard letter 	At randomization	Mosleh et al. 2009 Ohio Department of Health Bureau 2007
Primary Outcome	Dental exams 
 • Child's receipt of dental care 	Beginning and end of school year	ICDAS (Pitts 2004)
Secondary Outcomes (Mediators)	IPQ-RD 
 • Caregiver illness perception Caregiver Questionnaire 
 • Behavioral intention 	Baseline, Two-week, and Exit	Barrowclough et al. 2001 Ajzen 2002; Conner & Armitage 1998
Moderators	Caregiver Questionnaire 
 • Caregiver literacy • Caregiver self-efficacy² • Caregiver dental fear • Caregiver perceived stress • Subjective norm² • Dental insurance status Site (urban/rural)	Baseline	Bennett et al. 2003 Finlayson et al. 2005 Humphris et al. 1995 Cohen & Williamson 1988 NHANES IV Ohio, Washington
Confounders	Child's age, race, dental visit Caregiver socio-demographics (age, race, SES, education, marital status)	Baseline	NHANES IV
Subject compliance with Intervention	
 • Whether the referral letter (and DIG) was received (generic code) • Whether the referral letter (and DIG) was read/understood (Postcard) 	Within 2 days after Baseline dental exam	

1. **Baseline:** prior to screening dental exam; **At randomization:** after baseline dental screening exam; **Two-weeks:** Two weeks after randomization; **Exit:** two weeks before end of school year dental exam

2. Caregiver self-efficacy and subjective norms will also be considered as potential **mediators** in the additional mediational analyses, and will be measured at the **Exit** in addition to **Baseline**.

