Arm 4: The intervention is the reduced CSM referral letter + reduced dental information guide (Reduced DIG; MOP Appendices Section 6) to reinforce/change illness perception, knowledge about dental caries, and resources to seek care. The reduced dental information guide is a brochure with illustrations that provides myths and facts about dental caries, hints for getting dental care, making appointments and Medicaid access, transportation and dentist availability resources. As with the reduced letter, text and illustrations related to the “timeline” construct have been removed in the reduced dental information guide. This version will allow for an estimate of the effect of the “timeline” text and illustrations. While the general information on dental caries is similar for both sites, other resource information on how to seek care and a list of dentists is adapted to the specific site (see MOP Appendices Section 6 for site-specific DIG). The letter will be sent home with the child on the day of the screening and mailed to the caregiver’s address within 24 hours.

Arm 5: The control is the modified standard referral letter (based on November 2007 guidelines for Oral Health Screening in Ohio Schools. MOP Appendices Section 6). This letter is consistent with others used across the country. Both Ohio and Washington sites will use the same standard letter. As with Arms 1, 2, 3 and 4, the letter will be sent home with the child on the day of the screening and mailed to the caregiver’s address within 24 hours.

Table 6.1.1 Text of intervention letter and associated CSM constructs

Intervention letter text	CSM construct
Cavities are the #1 childhood health problem . Children may have cavities even if they do not have pain . Cavities should be treated when found.	Identity
Cavities can be serious in baby teeth. Cavities can affect children’s learning and how they look and feel about themselves .	Consequences
Other health problems may not be under your control. But, you can prevent cavities by taking your child to the dentist at least once a year . Your child will benefit from this greatly.	Controllability
Cavities do not just happen. Bacteria cause cavities. A dentist can clear up the bacteria.	Causes
If cavities are not treated, the bacteria in baby teeth can affect adult teeth .	Timeline

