With regard to our secondary endpoint, the overall IPQ-RD score, we note that our expected sample size will provide for each site 80% power to detect an 10 point decrease in the mean score (e.g., from an expected mean of 127 for the standard letter to 117 for the CSM referral letter) assuming a common standard deviation of 27 (estimated from previous data). A decrease in IPQ-RD scores indicates better illness representation/perception of caregiver. Since the IPQ-RD has never been utilized previously, we refer to a popular rule of thumb (Cohen, 1988) which considers the above standardized effect size of 0.37 (10/27) as a medium, and thus plausible, effect size.

The statistical test of the effect of the targeted component (timeline) will involve a comparison of 408 (Arm 1, 2) versus 48 (Arm 3, 4) subjects. This test may have low power, particularly if the effect of the targeted text is not large. However, including these arms will allow this effect to be estimated and thus provide some idea of its relative contribution in this exploratory analysis, as well as allow us to detect a large effect (if the component is responsible for a large proportion of the CSM referral letter effect).

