11. Cavities in my child has a big effect on how others see me .	1	2	3	4	5
12. Cavities in my child has caused money problems for me .	1	2	3	4	5
13. Cavities in my child has a big effect on my self-worth.	1	2	3	4	5

About your child:	Strongly Agree	Agree	Neither Agree nor Disagree	Disagree	Strongly Disagree
	1	2	3	4	5
14. There is a lot that can be done to improve the cavities in my child .	1	2	3	4	5
15. My child's treatment will help make his/her cavities better.	1	2	3	4	5
16. Improvement in my child's cavities is not due to chance or fate.	1	2	3	4	5
17. What my child does decides if his/her cavities get better or worse.	1	2	3	4	5

About you:	Strongly Agree	Agree	Neither Agree nor Disagree	Disagree	Strongly Disagree
	1	2	3	4	5
18. There is a lot I can do to control my child's cavity symptoms.	1	2	3	4	5
19. What I do decides if my child's cavities get better or worse.	1	2	3	4	5
20. There is a lot I can do to stop my child's cavities once they start.	1	2	3	4	5
21. There is a lot I can do to prevent cavities in my child.	1	2	3	4	5

Site: _____ ID# _____

About your child:

22. My child's cavities will not get better over time.
 23. Cavities in my child are likely to be long-lasting rather than short-term.

	Strongly Agree	Agree	Neither Agree nor Disagree	Disagree	Strongly Disagree
22.	1	2	3	4	5
23.	1	2	3	4	5

About your child:

24. Cavities in my child may change from time to time.
 25. There will be times when my child's cavity symptoms get worse and times when they get better.

	Strongly Agree	Agree	Neither Agree nor Disagree	Disagree	Strongly Disagree
24.	1	2	3	4	5
25.	1	2	3	4	5

About you:

26. I have a clear understanding of my child's cavities.
 27. My child's cavity symptoms are not confusing to me.

	Strongly Agree	Agree	Neither Agree nor Disagree	Disagree	Strongly Disagree
26.	1	2	3	4	5
27.	1	2	3	4	5

About you:

28. I get really sad and upset when I think about my child suffering from cavities.
 29. Seeing my child with cavities worries me.
 30. Seeing my child with cavities makes me feel angry.
 31. Seeing my child with cavities can make me feel helpless.

	Strongly Agree	Agree	Neither Agree nor Disagree	Disagree	Strongly Disagree
28.	1	2	3	4	5
29.	1	2	3	4	5
30.	1	2	3	4	5
31.	1	2	3	4	5

Site: _____ ID# _____

32. Causes of children's cavities:

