We would like to know what you think caused your child's cavities. There is no correct answer. We are interested in your own ideas about the causes of your child's cavities rather than what others (including doctors or family) may have told you. Below is a list of possible causes.

Please tell us how much you agree or disagree with each cause by circling the number that best fits your answer: *strongly agree (1), agree (2), neither agree nor disagree (3), disagree (4), strongly disagree (5)*.

Please circle the number of the best answer	Strongly Agree	Agree	Neither Agree nor Disagree	Disagree	Strongly Disagree
	1	2	3	4	5
32a. Stress or worry caused my child's cavities					
32b. Cavities runs in my family					
32c. A germ or virus caused my child's cavities					
32d. Diet or eating habits caused my child's cavities					
32e. Chance or bad luck caused my child's cavities					
32f. Poor dental care caused my child's cavities					
32g. Something I did as a parent caused my child's cavities					
32h. My negative thoughts caused my child's cavities					
32i. Family problems or worries caused my child's cavities					
32j. My feelings (feeling down, anxious) caused my child's cavities					
32k. My child's lack of ability to fight off infections caused his/her cavities					

Site: _____ ID#_____

33. Please list in order the three most important things that you now believe caused YOUR child's cavities. You may use any of the items from the previous question or you may have other ideas of your own.

The most important causes for me are:

1st _____

2nd _____

3rd _____

Family Access to Dentist Study

Caregiver Questionnaire	June 29, 2015
	Baseline

1

99

Study Site _____ ID# _____

Caregiver Questionnaire-Baseline

Date of Interview: _____
month day year

Interviewer's initials: _____

1. BACKGROUND INFORMATION**1.1 Your Age** _____ years**1.2 Your race and ethnicity.****1.2a Your race.** _____**1.2b Your ethnicity.** _____

Please mark with an X all that apply.

Please mark only one with an X.

Black _____

Not Hispanic/Latino _____

White _____

Hispanic/Latino _____

Asian _____

Unknown _____

Am. Indian/Alaskan _____

Hawaiian/Pacific Isl. _____

More than one race _____

Unknown _____

1.3 Your marital status.

Please mark only one with an X.

Married _____

Single _____

Common law _____

Divorced _____

Separated _____

Widow _____

Unknown _____

Study Site _____ ID# _____

Caregiver Questionnaire-Baseline

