32d. Diet or eating habits can cause cavities in a child	1	2	3	4	5
32e. Chance or bad luck can cause cavities in a child	1	2	3	4	5
32f. Poor dental care can cause cavities in a child	1	2	3	4	5
32g. Something a parent/caregiver does can cause cavities in a child	1	2	3	4	5
32h. A parent/caregiver's negative thoughts can cause cavities in a child	1	2	3	4	5
32i. Family problems or a parent/caregiver's worries can cause cavities in a child	1	2	3	4	5
32j. A parent/caregiver's feelings (feeling down, anxious) can cause cavities in a child	1	2	3	4	5
32k. A child's lack of ability to fight off infections can cause cavities	1	2	3	4	5

Site: _____ ID#_____

33. Please list in order the three most important things that you believe cause cavities in children. You may use any of the items from the previous question or you may have other ideas of your own.

[figure not shown]
The most important causes for me are:

1st _____

2nd _____

3rd _____

Family Access to Dentist Study

Study Site: _____ ID#: _____

Caregiver Questionnaire-2-week Follow-up

1. TAKING YOUR CHILD TO THE DENTIST**1.1 Did your child visit the dentist after the school dental screening?**

- a) Yes → Please GO TO Question 1.2
- b) No, but I have made an appointment with the dentist → Please SKIP TO Question 1.5
- c) No, and I have not made an appointment with the dentist → Please SKIP TO Question 1.6

If you answered YES to Question 1.1 above, please answer the following questions:

1.2 What is the name of the dental clinic / dentist where you took your child?

1.3 Did you take the referral letter (from the school dental screening) with you to the dentist?

- a) Yes
- b) No

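### IPQ-RD item 32e is keyed against the letter's own message on causes, so a letter that works can raise a score the plan reads as lower-is-better

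*Combined protocol and SAP*

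**What the plan says.** Section 3.2.2 makes change in the overall IPQ-RD and in the "cognitive (identity, consequences, timeline, cause, cure/controllability) representation subscale scores" the first secondary outcome and a mediator. It gives one direction, "A decrease in IPQ-RD scores (i.e. lower score) indicates better illness representation/perception", and exempts no item or subscale. Section 12.2 repeats it: "A decrease in IPQ-RD scores indicates better illness representation/perception of caregiver". Section 12.4 states no direction. It regresses the mean response on intervention group, for the whole questionnaire and for each of the five cognitive constructs, and mentions no reversal of items.

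In the Appendix C questionnaires, items 1a-1e are Yes/No. Items 2-31 and 32a-32k are five-point items running from 1 (strongly agree) to 5 (strongly disagree). At baseline the chance item reads "32e. Chance or bad luck caused my child's cavities"; at the two follow-ups (English forms) it reads "32e. Chance or bad luck can cause cavities in a child". Table 6.1.1 in section 6.1 maps the letter's wording "Cavities do not just happen. Bacteria cause cavities" to the Causes construct.

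Section 12.2 plans for a 10-point fall in the overall score, from 127 to 117 with SD 27, and claims 80% power per site.

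**The concern.** Applied to the printed coding, the stated direction gives item 32e the wrong sign. A caregiver persuaded by the letter moves towards disagreement on 32e. That raises the item score, and the plan calls the rise a worse perception. By contrast, item 32c (germ or virus) falls when the same message is accepted. The two cause items on which the letter's Causes text bears most directly therefore pull against each other.

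At stake is the cause subscale, which is analysed separately, and to a lesser extent the overall score, which feeds the first version of the mediation model in 12.4. A corrected belief could be reported as no change or as deterioration.

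**Working it through.** **1. Sign of the items.** Favourable means lower (3.2.2, 12.2); 1 is strongly agree (Appendix C).

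| Item | Caregiver who accepts the Causes text | Score | Counted as |
|---|---|---|---|
| 32c, germ or virus | agrees | 1-2 | better |
| 32e, chance or bad luck | disagrees | 4-5 | worse |
| 32a, 32h, 32i, 32j (stress, negative thoughts, family problems, feelings) | may disagree, by implication only | 4-5 if so | worse if so |
| 32b, 32d, 32f, 32g, 32k | ambiguous, or arguably keyed as intended | – | – |

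A one-category move on both 32c and 32e cancels. If only 32e moves by one category, the 11-item cause mean rises by 1/11 = 0.09. A full swing from 1 to 5 raises it by 4/11 = 0.36.

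**2. Are the causes in the total?** The item set is not stated, so check it against the planned mean of 127 and SD of 27.
- Items 2-25 (24 items) reach at most 24 × 5 = 120. Adding five identity items coded 1/2 gives a range of 29 to 130. The largest possible SD at mean 127 is then √[(130 − 127)(127 − 29)] = √294 = 17.1, below 27.
- Items 2-31 without causes: 127/30 = 4.23 per item. This is possible, but it means an average above disagree.
- Items 2-25 plus 32a-k: 127/35 = 3.6 per item. Items 2-31 plus 32a-k: 127/41 = 3.1 per item.

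The planning figures are plausible only with the causes included.

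**3. The plan's own power figure.** Difference 10, SD 27, and 102 per main arm per site (330 × 17/55). Alpha 0.05 two-sided is stated for the primary tests and assumed here.
- SE = 27√(2/102) = 3.78. Power = Φ(10/3.78 − 1.96) = 75.3% (74.9% with the noncentral t).
- The stated 80% needs 115 per arm. This shortfall is a separate matter; 75% is the reference below.

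**4. Illustrative attenuation.** Assume that a consistently keyed scale of K items would fall 10 points, spread evenly, with SD unchanged. If m items move the wrong way, the net fall is 10(K − 2m)/K.

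| Opposed items | K | Net fall | Power, 102 per arm |
|---|---|---|---|
| 32e only | 41 | 10 × 39/41 = 9.51 | 71.1% |
| 32e only | 35 | 10 × 33/35 = 9.43 | 70.3% |
| five items | 41 | 10 × 31/41 = 7.56 | 51.6% |
| five items | 35 | 10 × 25/35 = 7.14 | 47.2% |

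In the 11-item cause subscale, an even shift keeps (11 − 2)/11 = 9/11 of its size with 32e opposed, and (11 − 10)/11 = 1/11 with all five opposed.

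**The case against.** **Printed response codes are not a scoring key.** The Manual of Procedures and a separate Statistical Analysis Plan are listed as supplemental and were not available, and either may hold one. The caregiver questionnaire's stress items (5a-5d) likewise mix favourable and unfavourable wording under one coding, with no key shown. This stands as a limit. However, the protocol itself fixes the direction of the score without exception. Items such as 16 and 27 are negatively phrased so that agreement is favourable, which suggests that no reversal was intended.

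**Only 32e is addressed by the letter.** Table 6.1.1 says nothing about stress, thoughts, family problems or feelings. The follow-up forms ask only what can cause cavities, and item 32 tells respondents that no answer is correct. This stands: the other four items are opposed by inference.

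**Item 16 is not the same belief as 32e.** It says that improvement in the child's "cavities is not due to chance or fate", whereas 32e asks about cause. This also stands. The point rests on the letter against 32e, and does not need item 16.

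**The 10-point fall may already be net.** Section 12.2 states it for the overall score, and no item-level effects are given. If it is net, planned power is not reduced further. At 204 per arm with sites combined, power is about 96% for 10 points, 94% for 9.5 and 80% for 7.5.

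**Part of the plan softens the effect.** Constructs are analysed separately, and 12.4 uses the overall average only in its initial mediation model before allowing component paths. That limits the harm to the total. It does not help the cause construct, where the conflict lies.

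**Conclusion.** The point holds for item 32e. The stated direction, applied to the printed coding, counts acceptance of the letter's message as a worse perception. The cause subscale, and to a lesser extent the total, can therefore move the wrong way when the letter works. On the even-shift illustration the loss in the total is small if 32e stands alone (about half a point, and 4-5 points of per-site power) and material if all five items are opposed (2.4-2.9 points, with power near 50%). Both figures depend on the even shift, an unchanged SD, the causes being in the total, and 10 points being the fall before any cancellation.

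A reader might infer that five items are definitely mis-keyed, that each moves 0.5-1 point, and that 25-50% of the planned fall is therefore cancelled, leaving 51% or 26% power. The documents do not support this: they give no item-level shifts, and the letter never mentions the content of four of the five items. Nor do they show that the mediated effect as a whole is biased towards zero, because later models separate the components. The primary outcome is unaffected.

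**What to change.** Before unblinding, put a scoring rule in 3.2.2 and 12.4, choosing one of two forms:

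- Leave the item 32 causes out of the overall IPQ-RD score and analyse them item by item. This fits the instruction to respondents that no cause is the correct answer.
- Reverse-score 32e (6 minus the response), together with any other cause item the team prespecifies as a misattribution, before forming any total or mean.

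In either case, list the items in the total and state the favourable direction for each subscale. If a key already exists in the Manual of Procedures or the separate analysis plan, cite it in 3.2.2 and confirm how it treats 32e. Choosing the key after results are seen would make the secondary and mediation analyses data-driven.

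The cost is a scoring rule and no new data. The 127 and 27 planning figures would need restating under the new key.
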